3.1.2 Duration of Trial Participation for Each Patient

The trial will consist of the following periods (further details are provided in the graphical trial design [[Figure 3-1](#)] and the SoE in [Section 13.2](#)):

- A screening period of up to 2 weeks.
- A 24-week, open-label treatment period, including a titration period and a maintenance period.
- A 7-day, post-treatment, safety follow-up period after the last dose of the study drug or after premature/permanent discontinuation from study drug treatment. This will be a phone contact, but could be a site visit if ongoing or new AEs emerge during the post-treatment period, if necessary.

At the end of the trial, patients should discuss with the investigator, in collaboration with their HCP, whether to continue on the Gla-300 or IDeg-100 treatment regimen or transition to an alternate antihyperglycemic therapy. Discussions and final decisions made should be clearly documented in the patients' source documents.

[figure not shown]
The maximum trial duration per patient will be 27 weeks. A detailed description of the assessments performed during each trial period and at each visit is provided in [Section 13.2](#).

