6.2.6 Adverse Events

The investigator is responsible for reporting all AEs that are observed or reported during the trial, regardless of their relationship to the study drug or their clinical significance. The investigator remains responsible for following up on all AEs that are serious, considered related to the study drug or procedures, or caused the patient to discontinue the study drug treatment and/or the trial.

All AEs (serious or nonserious) will be recorded from the signing of the ICF until the safety follow-up visit, patient's permanent discontinuation from the trial, or loss to follow-up ([Section 13.2](#)).

The definitions of AEs and SAEs are provided in [Section 13.5](#). The definition of an AESI is provided in [Section 6.2.6.2](#).

All SAEs and AESIs will be recorded and reported to the sponsor or designee immediately, and under no circumstance should this be longer than 24 hours of awareness, as indicated in [Section 6.2.6.5](#). The investigator will submit any updated SAE/AESI data to the sponsor or designee within 24 hours of receipt of the information.

After the AEs/SAEs (including AESIs) are initially reported, the investigator is required to proactively follow-up with each patient at subsequent visits/contacts. At the prespecified trial end date, all SAEs and AESIs will be followed up until resolution, stabilization, the event is

otherwise explained, or the patient is lost to follow-up (as defined in [Section 4.4.2](#)). Further information on follow-up procedures is provided in [Section 13.5.3](#).

Investigators are not obligated to actively seek information on AEs or SAEs after conclusion of the trial. However, if the investigator learns of any SAE, including a death, at any time after a patient has been discharged from the trial, and they consider the event to be reasonably related to the study drug or trial participation, the investigator must promptly notify the sponsor.

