8.7.6.1 Analysis of AEs

The observation period of safety data will be divided as follows:

- The pre-treatment period is defined as the time between the date of signed informed consent and the first injection of the open-label study drug.
- The on-treatment period (24-week on-treatment period) is defined as the time from the first injection of the open-label study drug up to 7 days after the last injection of the open-label study drug, regardless of the introduction of rescue therapy. The 7-day interval is chosen based on the half-life of the study drug (approximately 5 times the half-life of IDeg-100).
- The post-treatment period is defined as the time starting 8 days after the last injection of the open-label study drug (after on-treatment period).

The AE observations will be classified per the observation periods of safety data (as defined above) into:

- Pre-treatment AEs: AEs that developed or worsened, or became serious during the pre-treatment period.
- Treatment-emergent AEs (TEAEs): AEs that developed or worsened, or became serious during the on-treatment period.
- Post-treatment AEs: AEs that developed or worsened, or became serious during the post-treatment period.

All AEs will be coded to a “preferred term” (PT) and “high-level group term” (HLGT), “high-level term” (HLT) and primary “system organ class” (SOC) using the version of MedDRA currently in use by the sponsor at the time of database lock.

Adverse event incidence tables will present data by SOC (sorted by internationally agreed order), HLT, HLT, and PT sorted in alphabetical order for each treatment arm, as well as the number (n) and percentage (%) of patients experiencing an AE. Multiple occurrences of the same event in the same patient will be counted only once in the tables within a treatment

phase. The denominator for computation of percentages is the safety set within each treatment arm.

The AE incidence tables will be provided by treatment arm for all types of TEAEs: All TEAEs, all treatment-emergent SAEs, all TEAEs leading to permanent treatment discontinuation, and all TEAEs related to local tolerability at injection site, and hypersensitivity.

The following death summaries will be generated for the safety set:

- Number (%) of patients who died by trial period (TEAE periods, on-trial, post-trial) and reasons for death, summarized by treatment received.
- Death in nonrandomized patients or randomized patients who were not treated.

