- ^d An unscheduled visit can be planned anytime during the treatment period if study drug resupply is required. This will be a site visit or via phone contact with DTP-IMP delivery. The sponsor-approved courier company will need at least 72 hours’ notice to collect treatment kits from a trial site.
- ^e This will be a phone contact, but could be a site visit if ongoing or new AEs emerge during the post-treatment period, if necessary.
- ^f A physical examination will be performed per standard of care to assess the health status of patients. A list of assessments is provided in Section 6.2.1.
- ^g Study drug resupply at Visit 10 will be via phone contact with DTP-IMP delivery. The sponsor-approved courier company will need at least 72 hours’ notice to collect treatment kits from a trial site.
- ^h All patients will be trained by trial staff on how to use the pen correctly, how to store it, and how to change the needle to ensure that each patient is able to perform self-injection. An instruction leaflet will be provided to patients that explains how to use the disposable pen and needles. Training will be repeated during the treatment period as often as deemed necessary by site staff.
- ⁱ Gla-300 or IDeg-100 should be self-administered once daily between 6:00 PM and 8:00 PM throughout the treatment period. The investigator and patient will discuss and agree upon the injection time. Gla-300 or IDeg-100 will be administered after the fasting blood sample draw during site visits. The need for dose adjustment will be assessed at each visit.
- ^j For scheduled site visits, patients will be required to arrive having fasted without administering the study drug. Fasting is defined as no intake of food or drink, except water, in the 8 hours before blood sampling.
- ^k Fasting SMPG values will be used to titrate and adjust study drug doses and monitor glycemic levels. Patients will be required to measure fasting SMPG values (using the glucose meter supplied during the screening period) before breakfast and before administration of study drug once daily throughout the treatment period and to record the results in the eDiary.
- ^l The 7-point SMPG profile will be measured (and recorded in the patient’s eDiary) at the following 7 points: preprandial and 2 hours after starting breakfast, lunch, and dinner, and at bedtime. The 7-point SMPG profile will be performed over a single, 24-hour period, on at least 2 days within the week before selected site visits.

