13.3 Appendix: Patient eDiary Information

Patients will be provided with an eDiary to use during the trial, and site staff will instruct them on how to complete the eDiary. Training on eDiary use will be documented in the patient's source documents.

Patients are required to make eDiary entries at least once daily from the screening period (Visit 1) through the end of the treatment period (Visit 17) and bring completed eDiaries at each site visit. Site staff will verify the eDiary (at the time points specified in the SoE [[Section 13.2](#)]) by viewing the data transmitted from the eDiaries into the database.

The information to be recorded in the eDiary may include, but not be limited to, the following:

- Each dose of study drug taken (date/time and actual dose) and type and dose of daily background noninsulin antidiabetic drug(s). The patient will document any temporary treatment discontinuations.
- Fasting SMPG values (using the glucose meter supplied during the screening period) before breakfast and before administration of study drug once daily throughout the treatment period.
- 7-point SMPG profile: 7-point SMPG profiles measured at the following 7 points: preprandial and 2 hours after starting breakfast, lunch, and dinner, and at bedtime. The time points are specified in the SoE ([Section 13.2](#)).
- Symptoms of hypoglycemia: Patients will be trained on the hypoglycemia eDiary completion requirements and the need to contact the investigator as soon as possible in case of a significant hypoglycemia occurrence, so that appropriate actions can be taken (eg, intolerance to the study drug injection).
- If assistance to resolve the hypoglycemia event was required out of necessity or convenience.

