- The **pre-treatment period** (up to 2 weeks) is defined as the time between the date of signed informed consent and the first injection of the open-label study drug.
- The **on-treatment period** (24-weeks) is defined as the 24-week open-label treatment period. The on-treatment period includes a 12-week titration period where study drug doses will be adjusted using a recommended dose-adjustment algorithm, as well as a 12-week maintenance period at the titrated dose.
- The **post-treatment period** is defined as the 7-day, post-treatment, safety follow-up period after the last dose of the study drug or after premature/permanent discontinuation from study drug treatment.

The on-study period is defined as the time from the date of signed informed consent until the end of the study defined as the last scheduled visit for those who completed the study and the end-of-study date (“Status Date”) collected on electronic case report form (eCRF) page “Completion of End of Study” for those who did not complete the study. If death is the end-of-study reason, date of death will be used.

The observation period used for safety analyses is described in [Section 4.7](#).

The maximum trial duration per participant will be 27 weeks.

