4.7 SAFETY ANALYSES

All safety analyses will be performed on the safety population as defined in [Section 3](#), unless otherwise specified, using the common rules:

- The analysis of the safety variables will be essentially descriptive, and no formal hypothesis testing is planned.
- Safety data in participants who do not belong to the safety population (eg, exposed but not randomized) will be provided separately.

The observation period of safety data will be divided into 3 periods as defined below:

- **Pre-treatment period:** the time between the date of signed informed consent and the first injection of the open-label study drug.
- **On-treatment period:** the time from the first injection of the open-label study drug up to 7 days after the last injection of the open-label study drug, regardless of the introduction of rescue therapy. The 7-day interval is chosen based on the half-life of the study drug (approximately 5 times the half-life of IDeg-100).
- **Post-treatment period:** the time starting 8 days after the last injection of the open-label study drug.

The denominator for computation of percentages is the safety set within each treatment arm unless otherwise specified.

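### The −3 side of the Visit 18 window lets the last planned adverse event contact fall before the plan's own 7-day treatment-emergent window has closed

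*SAP*

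**What the plan says.** **The analysis window.** SAP 4.7 defines the on-treatment period as "the time from the first injection of the open-label study drug up to 7 days after the last injection of the open-label study drug", and Protocol 8.7.6.1 uses the same limits. Treatment-emergent AEs are "AEs that developed or worsened, or became serious during the on-treatment period". The 7 days have a stated reason: roughly five half-lives of IDeg-100.

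**The collection rule.** Protocol 6.2.6 says: "All AEs (serious or nonserious) will be recorded from the signing of the ICF until the safety follow-up visit", or until the patient leaves the trial or is lost. Under Protocol 13.3 the required eDiary entries end at Visit 17. Protocol 6.2.6.4 keeps SAEs reportable until 30 days after the last dose.

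**The schedule.** Protocol Tables 2 and 13-3 and SAP Table 13 put Visit 17 at Day 168 ±3 and Visit 18 at Week 25, Day 175 ±3. The visible Visit 18 footnote covers only the form of the contact: "This will be a phone contact, but could be a site visit if ongoing or new AEs emerge during the post-treatment period, if necessary". Footnote b, on the Visit row, is redacted.

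**The follow-up period in the text.** Protocol 3.1.2 and the synopsis describe "A 7-day, post-treatment, safety follow-up period after the last dose of the study drug". SAP 4.1 repeats this, but introduces those segments as serving non-safety analyses and refers to SAP 4.7 for safety.

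**The concern.** A treatment-emergent count should rest on collection that covers the whole of its own window. Here the window ends 7 days after the last injection, while collection of nonserious events ends at a call that may be made earlier. After Visit 17 that call is the only planned contact, and no other section collects new nonserious AEs after it. Events already reported are followed up (Protocol 6.2.6.8), but that does not find new ones.

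At stake are nonserious AEs and nonserious hypoglycemia in the last few days of the window, in patients who stay on drug to about Week 24. The treatment-emergent tables and a listing of on-treatment hypoglycemic events remain in the abbreviated report (SAP Appendix 6).

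**Working it through.** **Inputs.** Visit 17: Day 168 ±3. Visit 18: Day 175 ±3 (Protocol Table 13-3). Window closes at last injection + 7 days (SAP 4.7). Dosing is once daily between 6 and 8 PM, first dose on the evening of Day 0 (Protocol 5.5).

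**The plan's own figures.** 25 × 7 = 175, and 168 + 7 = 175. Counted from Day −14, 14 + 175 = 189 days = 27.0 weeks, which is the stated maximum.

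**Visit 18 tied to the last dose.** With Visit 18 = last dose + 7 + d and d from −3 to +3, days early = max(0, −d).
- The call falls on days +4 to +10 after the last dose.
- Days +4, +5 and +6 are 3, 2 and 1 days early, so 3 of the 7 permitted days are early.
- Mean over the permitted days: (3 + 2 + 1)/7 = 0.86 days, or 0.86/175 = 0.49% of a 175-day window.

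The anchor is present in this calculation. The shortfall comes from the −3 alone.

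**Both windows used independently, as printed.** Days early = max(0, (168 + d17 − o + 7) − (175 + d18)), which simplifies to max(0, d17 − d18 − o). Here d17 and d18 each run from −3 to +3 (49 pairs). The term o is 0 if the last dose is on the Visit 17 day and 1 if it is the evening before.

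| Last dose | Pairs early | More than 3 days early | Maximum | Mean |
|---|---|---|---|---|
| Evening before Visit 17 | 15 of 49 | 3 of 49 | 5 days (1 pair) | 35/49 = 0.71 days (0.41%) |
| On the Visit 17 day | 21 of 49 | 6 of 49 | 6 days (1 pair) | 56/49 = 1.14 days (0.65%) |

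The text does not settle o. A first dose on the evening of Day 0 makes the 168th daily dose fall on Day 167, which suggests the evening before. Protocol 4.4.1.1 (end-of-treatment procedures belong to the last dosing day) and the dosing footnote (dose after the blood draw at site visits) suggest the visit day. The means weight permitted days equally and do not forecast when calls are made.

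**Candidate fixes.**
- Last injection + 7, window 0 to +3: no shortfall in whole days. But doses are given in the evening, so a daytime call on day +7 leaves less than one day uncovered.
- Last injection + 8, window 0 to +3: the call is on day +8 or later, after day 7 is complete, so the shortfall is 0. The latest call is 171 + 8 + 3 = Day 182.

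**Duration from Day −14.** The present tables allow 14 + 178 = 192 days (27.4 weeks), already above 189. With the +8 fix, 14 + 182 = 196 days (28.0 weeks).

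**Reach.** The first randomization (20 December 2022) and the sponsor's stop (27 June 2023) are 189 days apart. Only participants randomized by 10 January 2023 (27 June minus 168 days) could have reached Day 168 by the stop date. The documents do not say whether anyone stayed on treatment after it.

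**The case against.** The strongest reply is that the timing rule is already in the protocol body. Protocol 3.1.2 describes a 7-day period after the last dose, and a site that treats those 7 days as a minimum leaves no gap. That is a fair reading. However, the tables that sites schedule from expressly permit 3 days less, so coverage depends on the site not using the printed tolerance.

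A reader might infer that the tables lack a last-dose anchor and that this causes the gap. The documents do not support that. Footnote b on the Visit row is redacted and Figure 3-1 is not shown, so the absence of an anchor cannot be confirmed. Restoring an anchor while keeping ±3 would still leave the 1 to 3 days. Nor is SAP 4.1 strong evidence of a safety anchor, since it labels its periods as non-safety.

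The 5- and 6-day figures are equally easy to over-read. Each is one pair in 49 and requires a site to ignore Protocol 3.1.2.

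The reply is also right about weight:
- SAEs are reportable to 30 days.
- Patients who stop drug early but stay in the trial are followed to the scheduled end (Protocol 4.4.1.1 and 4.4.3), so their last contact comes after their window closes.
- The safety analysis is descriptive, and exposure is counted only to the last dose (SAP 4.7.1 and 4.7.2).
- Hypoglycemia is summarized over the 24-week period.

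**Conclusion.** The point holds as a minor one. A site that follows the printed tolerance can make the last planned AE contact 1 to 3 days before the treatment-emergent window closes. With the Visit 17 and Visit 18 windows used independently, the extreme is 5 days (last dose the evening before Visit 17) or 6 days (last dose on the Visit 17 day). These are permitted days, not expected ones.

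The consequence is confined to nonserious AEs and nonserious hypoglycemia in patients treated to about Week 24, and it is very small. A reader might suspect a bias between arms, but both arms share one schedule and nothing in the documents points to one. No sample size, power or error-rate figure is touched. Early termination reduces the practical reach further.

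The conclusion assumes that the redacted footnote does not cancel the visible −3 tolerance.

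**What to change.** In Protocol Tables 2 and 13-3, replace Day 175 ±3 for Visit 18 with last injection + 8 days and a window of 0 to +3 days. At that call, ask about AEs and hypoglycemia through day 7 after the last injection. For a last dose on Day 167 or 168 the target is Day 175 or 176, so the call stays at about Week 25.

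Restate the maximum duration as about 28 weeks wherever 27 appears: the Protocol synopsis, Protocol 3.1 and 3.1.2, and SAP 1.1 and 4.1 ("The maximum trial duration per participant will be 27 weeks"). SAP 4.7 stays as it is. SAP Table 13 should match for consistency only, since that SAP was approved on 17 October 2023, after the trial stopped. The practical use now is for any protocol built on this schedule.

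The cost is a call window of 4 permitted days in place of 7, and a latest call on Day 182 instead of Day 178, 4 days later. No visit or procedure is added.

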4.7.1 Extent of exposure

The extent of IMP exposure will be assessed by the duration of IMP exposure, compliance, and dose and summarized within the safety population.

Duration of IMP exposure

Duration of IMP exposure (in days) is defined as last IMP administration date - first IMP administration date +1 day, regardless of unplanned intermittent discontinuations. If the date of the last dose of IMP is missing, the duration of IMP will be left as missing.

Duration of IMP exposure (in weeks) is defined as (Last day of exposure - first day of exposure +1)/7. Duration of IMP exposure (in weeks) will be summarized quantitatively using descriptive statistics and categorically as below:

- ≤ 12 weeks
- > 12 weeks to ≤ 24 weeks
- > 24 weeks

Additionally, cumulative duration of treatment exposure expressed in participant-years will be calculated, defined as the sum of days of the duration of treatment exposure for all participants divided by 365.25.

Treatment compliance

A given administration will be considered noncompliant if the participant did not receive a once daily administration between 6:00 AM and 8:00 PM as required by the protocol. No imputation will be made for participants with missing or incomplete data.

Percentage of treatment compliance for a participant will be defined as the number of injections that the participant was compliant divided by the total number of injections that the participant was planned to take from the first administration of IMP up to the actual last administration of IMP multiplied by 100.

The number of planned injections is equal to the duration of IMP exposure (in days).

Treatment compliance will be summarized quantitatively using descriptive statistics and will also be summarized categorically: <60%, ≥60% to <80%, ≥80% to ≤100%, >100%.

Cases of overdose will constitute AESIs and will be listed as such.

Dosing

During the trial, the dose of study drug (Gla-300 or IDeg-100) will be titrated for each participant to achieve glycemic targets without hypoglycemia using a dose-adjustment algorithm. After randomization, the dose is titrated at least weekly (but no more than every 3 days) until the participant reaches a target fasting SMPG value of 80 to 100 mg/dL (4.4 to 5.6 mmol/L) while avoiding hypoglycemia episodes. Best efforts should be made to reach the glycemic target by 8-12 weeks after randomization. Thereafter, until the end of the trial, the doses of Gla-300 and IDeg-100 will be adjusted to maintain this glycemic target, if deemed appropriate by the investigator. Dose adjustments will be based on the median value of fasting SMPG values from the last 3 measurements, including the value on the day of titration, measured by the patient using glucose meters and accessories supplied by the sponsor through a vendor.

Mean daily insulin doses received by each participant will be summarized descriptively at the end of the titration period (Week 12) and the end of the maintenance period (Week 24). The mean daily insulin dose is calculated as the mean of daily insulin doses collected over the 7 days preceding the visit. If less than 4 days of daily dosing data are available for a participant in the 7-day period preceding the timepoint, the mean daily insulin dose for that participant will be reported as missing.

The frequency and percentage of participants requiring dose adjustments after Week 12 will be presented.

A box plot of mean daily insulin dose at the end of the titration period (Week 12) and the end of the maintenance period (Week 24), will be produced, as well as a bar chart presenting the percentage (%) of participants requiring dose adjustments after Week 12.

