Study Drug, Dosage, and Route of Administration:	
The study drugs are Gla-300 or IDeg-100 and will be supplied as prefilled, disposable pens (Gla-300 as a SoloStar® pen and IDeg-100 as a FlexTouch® pen).
 
• Formulation:
○ Gla-300 will be supplied as a sterile, nonpyrogenic, clear, colorless solution in a SoloStar prefilled (disposable) pen for subcutaneous (SC) injection.○ IDeg-100 will be supplied as a sterile, nonpyrogenic, clear, colorless solution in a FlexTouch prefilled (disposable) pen for SC injection.• Unit dose strength(s)/Dosage level(s):
○ Gla-300: Each Gla-300 SoloStar pen contains 450 U of insulin glargine (1.5 mL of 300 U/mL insulin glargine solution).○ IDeg-100: Each IDeg-100 FlexTouch pen contains 300 U of insulin degludec (3 mL of 100 U/mL insulin degludec solution).• Route of administration: The study drug will be administered via SC self-injection into the abdominal area, thigh, or upper arm using the SoloStar pen or FlexTouch pen. Injection sites should be rotated within the same region from 1 injection to the next to reduce the risk of lipodystrophy.• Time of administration: Gla-300 or IDeg-100 should be self-administered once daily between 6:00 PM and 8:00 PM throughout the treatment period. The investigator and patient will discuss and agree upon the injection time at Visit 2 (baseline/randomization).
---	---

Starting Dose

Per the product label, in insulin-naïve patients with T2DM, the recommended starting dose of Gla-300 is 0.2 U/kg of body weight once daily and the recommended starting dose of IDeg-100 is 10 U once daily.

Dose Modifications

During the trial, the dose of study drug will be titrated to achieve glycemic targets without hypoglycemia using the recommended dose-adjustment algorithm ([Table 1](#)).

- After randomization, the dose will be titrated at least weekly (but no more than every 3 days) until the patient reaches a target fasting SMPG value of 80 to 100 mg/dL (4.4 to 5.6 mmol/L) while avoiding hypoglycemia episodes.

- Thereafter, until the end of the trial, the doses of Gla-300 and IDeg-100 will be adjusted to maintain this glycemic target, if deemed appropriate by the investigator.

Best efforts should be made to reach the glycemic target by 8-12 weeks after randomization.

Table 1 Recommended Dose-Adjustment Algorithm

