5.5 Treatments Administered

The following treatments will be administered in the trial:

- Gla-300 arm: Insulin glargine 300 U/mL
- IDeg-100 arm: Insulin degludec 100 U/mL
- Time of administration:
 - Gla-300 or IDeg-100 should be self-administered once daily between 6:00 PM and 8:00 PM throughout the treatment period. The investigator and patient will discuss and agree upon the injection time at Visit 2 (baseline/randomization).
 - The first dose of Gla-300 or IDeg-100 will be administered on the evening of Day 0 (Visit 2).

Starting Dose

Per the product label, in insulin-naïve patients with T2DM, the recommended starting dose of Gla-300 0.2 U/kg of body weight once daily and the recommended starting dose of IDeg-100 is 10 U once daily.

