5.2 APPENDIX 2 CHANGES TO PROTOCOL-PLANNED ANALYSES

Changes to protocol-planned analyses include the following:

- Multiplicity adjustments on secondary endpoints ([Section 4.1](#), [Section 4.4.1.2](#), [Section 4.6](#)).
- ~~CCI~~ compliance rules ([Section 4.5.1](#)).
- Analysis of exploratory endpoints - ~~CCI~~ ([Section 4.5.2](#)).

Due to study early termination, planned analyses have been reduced in accordance with an abbreviated CSR. The list of tables, listings and figures supporting the abbreviated CSR are documented in Appendix 6 ([Section 5.6](#)) and focus on demographics, disease characteristics at baseline, exposure, participant disposition and safety. Primary and secondary efficacy data is descriptively summarized.

5.3 APPENDIX 3 DEMOGRAPHICS AND BASELINE CHARACTERISTICS, MEDICAL (OR SURGICAL HISTORY), DISEASE CHARACTERISTICS AT BASELINE, PRIOR AND CONCOMITANT MEDICATIONS

The following demographics and baseline characteristics, medical and surgical history and disease characteristics at baseline, and prior and concomitant medications will be summarized for the ITT population. Continuous data will be summarized using descriptive statistics. Categorical data will be summarized using counts and percentages.

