5.6 APPENDIX 6 TABLE OF CONTENTS FOR ABBREVIATED CSR

	Title	Analysis Set
Table		
14.1.1.1	Participant Disposition	ITT Set
14.1.1.2	Analysis Sets	Screened Set
14.1.1.3	Number of Participants Screened	Screened Set
14.1.1.4	Number of Participants Screened by Country and Site	Screened Set
14.1.2	Significant Protocol Deviations	ITT Set
14.1.3.1	Demographics and Participant Characteristics at Baseline	Safety Set
14.1.3.2	Disease Characteristics at Baseline	Safety Set
14.1.4	Medical or Surgical History at Screening by Primary SOC and PT	ITT Set
14.1.5.1	Extent of Study Treatment Exposure	Safety Set
14.1.5.2	Treatment Compliance	Safety Set
14.1.5.3	Dosing Summary	Safety Set
14.2.1.1	Baseline Summary of Primary Endpoint: HbA1c Level	ITT Set

	Title	Analysis Set
14.2.1.2	Baseline Summary of Primary Endpoint: HbA1c Level by Subgroups	ITT Set
14.2.2.	Baseline Summary of Secondary Endpoints	ITT Set
14.3.1	Overview of Adverse Event profile: Treatment-emergent Adverse Events	Safety Set
14.3.2	Number (%) of Participants with TEAE(s) by Primary SOC, HLGT, HLT and PT	Safety Set
14.3.3.	Participants with a Common TEAE ($\geq 5\%$) in Any Treatment Group by Primary SOC, HLGT, HLT and PT	Safety Set
14.3.4	Number (%) of Participants with TEAE(s) Related to IMP as per Investigator's Judgment by Primary SOC and PT	Safety Set
14.3.5	Number (%) of Participants with Treatment-emergent SAEs by Primary SOC and PT	Safety Set
14.3.6	Number (%) of Participants Who Died by Study Period	Safety Set
14.3.7	Overview of Hypoglycemic Events Overall and by Observation Period, ADA Level, and Diurnal Distribution	Safety Set
Figure		
14.2.1.1	Box Plot of HbA1c Level by Analysis Visit (Observed Cases)	ITT Set
14.2.2.1	Box Plot of FPG Level by Analysis Visit (Observed Cases)	ITT Set
14.2.2.2	Box Plot of SMPG Level by Analysis Visit (Observed Cases)	ITT Set
14.2.2.3	Line Plot of 7-point SMPG Profiles, Per Time Point within 24-Hour Period by Analysis Visit (Observed Cases)	ITT Set
14.2.2.4	Bar Chart of Percentage (%) of Participants Reaching HbA1c $< 7.0\%$ at Week 24 (Observed Cases)	ITT Set
Listing		
16.2.1	Participant Randomization List	ITT Set
16.2.2	Listing of Participants with at Least One Protocol Deviation	ITT Set
16.2.3.1	Listing of Participant Demographics	Safety Set
16.2.3.2	Listing of Baseline Disease Characteristics	Safety Set
16.2.5.1	Exposure to IMP	Safety Set
16.2.7.1	Listing of all AEs	Safety Set
16.2.7.2	Listing of all AEs leading to study discontinuation	Safety Set

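### SAP 4.7.1 counts injections from 6:00 AM to 8:00 PM as compliant, but the protocol window is 6:00 PM to 8:00 PM, so reported compliance can only be raised or left unchanged

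*SAP*

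**What the plan says.** Under Treatment compliance, SAP 4.7.1 calls an administration noncompliant if the "participant did not receive a once daily administration between 6:00 AM and 8:00 PM as required by the protocol". A participant's compliance percentage is then "the number of injections that the participant was compliant divided by the total number of injections that the participant was planned to take", times 100. The planned number equals the days of exposure, and the result is also tabulated as below 60%, 60% to below 80%, 80% to 100%, and above 100%.

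Protocol 5.5 reads: "Gla-300 or IDeg-100 should be self-administered once daily between 6:00 PM and 8:00 PM throughout the treatment period". It adds: "The first dose of Gla-300 or IDeg-100 will be administered on the evening of Day 0 (Visit 2"). The protocol synopsis and footnote i of the protocol's schedule of events give the same hours: "once daily between 6:00 PM and 8:00 PM throughout the treatment period". Footnote i of the SAP's own schedule (Section 5.7.1, Table 13) repeats them.

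SAP Appendix 2 (Section 5.2) lists the departures from the protocol-planned analyses. Its one visible item on "compliance rules" points to Section 4.5.1, on exploratory endpoints, not to 4.7.1. Appendix 6 (Section 5.6) keeps Table 14.1.5.2, "Treatment Compliance", for the abbreviated CSR.

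**The concern.** The SAP credits the protocol with a window that the protocol does not contain, and contradicts its own schedule footnote. The place matters more than the slip. The clock window is the only test the SAP gives for whether an injection counts as compliant, and it feeds the numerator of the percentage directly. A programmer who follows the text would count a 9:00 AM injection as compliant in a trial that instructs evening dosing.

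At stake is how a reader of the CSR judges adherence to the instructed injection time. Both arms share the rule, so nothing in it favours one insulin by design, but the level of compliance reported in either arm could be too high.

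**Working it through.** No sample-size or power figure is involved. The check compares the two windows and applies the SAP's own formula under each.

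**Inputs**
- SAP window (SAP 4.7.1): 06:00 to 20:00, which is 14 hours.
- Protocol window (Protocol synopsis, 5.5 and schedule footnote i; SAP 5.7.1 footnote i): 18:00 to 20:00, which is 2 hours.
- Denominator (SAP 4.7.1): exposure days, the same under either window.
- Illustration: 24 weeks × 7 = 168 planned injections, a full course.
- Assumed, because the documents give no injection times: d, the share of planned injections taken from 6:00 AM up to 6:00 PM.

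**Direction.** The SAP window is 14 / 2 = 7 times as wide and adds 14 − 2 = 12 hours. Every time from 18:00 to 20:00 also lies within 06:00 to 20:00. Counting injection by injection, the SAP numerator is therefore never smaller than the protocol numerator:

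SAP compliance − protocol-window compliance = d, with d ≥ 0.

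Equality holds only when no injection falls between 6:00 AM and 6:00 PM. As a check, 300 simulated participants over 168 days with random injection times gave no day on which the SAP window counted fewer injections.

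**Size in percentage points**

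| Assumed d | Injections out of 168 | Added to compliance |
|---|---|---|
| 0% | 0 | 0 points |
| 5% | 8.4 | 5 points |
| 10% | 16.8 | 10 points |
| 20% | 33.6 | 20 points |

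The logical extreme is a participant who injects every morning: 100% under the SAP text and 0% under the protocol.

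**Size in categories.** The 80% cut needs 135 compliant injections (135 / 168 = 80.4%), since 134 / 168 = 79.8% falls short. The number of daytime injections that puts a participant in the 80% to 100% category, when the protocol window would put them in the one below, is 168 − (noncompliant under both windows) − 134:

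| Noncompliant under both | Daytime injections needed | SAP compliance | Protocol-window compliance |
|---|---|---|---|
| 0 | 168 − 0 − 134 = 34 (20.2%) | 168 / 168 = 100% | 79.8% |
| 8 | 168 − 8 − 134 = 26 (15.5%) | 160 / 168 = 95.2% | 79.8% |
| 17 | 168 − 17 − 134 = 17 (10.1%) | 151 / 168 = 89.9% | 79.8% |

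**Reach.** The primary HbA1c analysis (SAP 4.3.2) does not use the percentage. Exclusions from the per-protocol set come from a blinded case-by-case review of deviations (SAP 4.2). Hypoglycemia timing (SAP 4.7.2) and the dose summaries (SAP 4.7.1, Dosing) have their own definitions.

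**The case against.** The strongest reply is that this is a one-letter slip. The sentence defers to the protocol, the SAP's own footnote has the right hours, and nothing suggests that anyone chose a 14-hour window. Harm needs two further things that the documents do not establish: that the slip was programmed literally, and that some participants injected in the daytime. Participants agreed an evening time and took their first dose in the evening. Injections that run past 8:00 PM fail under both windows, so a sustained 20% daytime share would be extreme. All of this stands. It limits the likely size, but does not make the rule correct as written.

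The 168-injection counts also need care. The first randomization was on 20 December 2022 and the sponsor terminated the trial on 27 June 2023, 189 days later. Unless treatment continued after termination, only participants randomized by about 10 January 2023 could have completed 168 days. The counts are a full-course illustration; the result that the overstatement equals d does not depend on duration.

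The direction depends on how the rule is read. If it demanded exactly one injection inside the window each day, a participant with one dose at 8:00 AM and another at 7:00 PM would fail under the SAP window and pass under the protocol's, and compliance would be understated. The SAP counts compliant injections and provides a category above 100%, so counting by injection fits better. Even then, extra daytime doses could move someone into the category above 100%, which is a higher figure but not a more favourable one.

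**Conclusion.** The concern holds. The compliance window in SAP 4.7.1 is wrong: it is seven times as wide as the window it claims to take from the protocol, and no change is declared. Counted by injection, literal use overstates each participant's compliance by the share of planned injections taken from 6:00 AM up to 6:00 PM, or leaves it unchanged if there were none. That share is unknown; the 0 to 20 point range rests on assumed values. The consequence is limited to Table 14.1.5.2, which is descriptive. It should be corrected because that table is kept in the abbreviated CSR, but no efficacy or hypoglycemia result depends on it.

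**What to change.** In SAP 4.7.1, change 6:00 AM to 6:00 PM. Check which window the program for Table 14.1.5.2 used, and rerun the table only if it was the 14-hour one. The rerun should need no new data: Protocol 13.3 lists "Each dose of study drug taken (date/time and actual dose") among the information the eDiary may hold, so confirm that the times were in fact captured.

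The cost is a one-word correction, one program check and at most one rerun table. The only downside is that reported compliance may look less favourable.
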